- To determine if patient-reported nausea and vomiting at post-operative days 1, 3, 5, 10, and 30 is significantly decreased in patients in the study group.
- To measure the rate of block-related complications in the study group. Potential complications include local anesthetic toxicity, intravascular injection, persistent weakness or paresthesia, nerve injury, voiding dysfunction, persistent numbness, altered sexual function, bleeding/hematoma, hypotension, infection at the injection site, or other complaints related to the block.
- To determine if narcotic requirements postoperatively are lower in the study group. To determine total anesthetic and operative time, as well as costs.

Background and Significance:

Living kidney donors are carefully screened prior to recommending kidney donation. They are informed of the risks of surgery and the option of changing their mind until the day of kidney donation. All of the patients have an abdominal and pelvic CT scan to evaluate the renal anatomy and to screen for abnormalities. Our goal is to make the operation as minimally invasive as possible and to facilitate the return to normal function as quickly as possible. Currently, most patients need narcotics to control the pain after surgery. These medications can have significant side effects including nausea and constipation, which can delay recovery from the operation.

Since the first successful living donor kidney transplant between identical twins, the special nature of this operation and the anesthetic management has been debated (1). Extensive efforts have been made to improve the safety and reduce the morbidity of kidney donation. At UCLA, laparoscopic kidney donation was introduced in 1999, and is now the standard of care for approximately 150 of these operations annually. Ketorolac analgesia was added to reduce pain in 2002 and the procedure has continued to evolve to promote return to normal function as soon as possible (2). The median length of stay for these patients is currently 1.4 days.

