A review of the literature identified three publications with enhanced recovery from surgery (ERAS) protocols. The Univ. of Michigan protocol uses a transversus abdominus plane (TAP) block under ultrasound guidance using a hydrodissection technique with normal saline followed by 15 to 20 mL of 0.5% ropivacaine per side with length of stay (LOS) of 1 day after surgery (3). The Duke protocol uses a liposomal bupivacaine TAP block and a hand assisted approach, which also achieved a one day LOS (4). A randomized study of hand assisted laparoscopic kidney donation at the Univ. of Minnesota compared bupivacaine to liposomal bupivacaine for subcostal TAP block which showed a significant reduction in pain scores for the liposomal bupivacaine 24-48 hours after surgery, but a LOS of 2-3 days in both groups (5).

An alternative local anesthetic approach in laparoscopic gynecologic operations and pediatric pyeloplasty is the transmuscular quadratus lumborum (TQL) block. The most important advantage of TQL block over TAP block is a consistent posterior spread of local anesthetic up to the paravertebral space (6). In preliminary studies, we have placed a TQL block in 6 patients using bupivacaine and methylene blue. These patients had excellent pain relief for approximately 12 – 18 hours, but then had more need for outpatient narcotics after the local anesthetic effect wore off. In patients with bupivacaine TAP block, placed either by ultrasound, or by direct visualization with the laparoscope, pain relief is achieved for the anterior abdominal wall, but patients still need narcotics for relief of pain toward the back. Complications that have been reported with TQL block include hypotension which may have been due to sympathetic blockade, and motor dysfunction of the leg for over 24 hours (7,8). Based on our minimal experience with TQL block and review of the literature, it is our hypothesis that the optimal pain management for fully laparoscopic donor nephrectomy is a combined TQL block placed after the induction of anesthesia and a TAP block placed after the midline incision is closed using a long acting local anesthetic.

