Liposomal bupivacaine is a novel local anesthetic designed for prolonged pain relief, up to 72 hours. Despite its long-acting analgesic potential, liposomal bupivacaine is significantly more expensive than other local anesthetic alternatives. The primary aim of this investigation is to examine whether or not liposomal bupivacaine provides superior pain relief, clinically significant

opioid-sparing effects, and improved patient satisfaction versus a control group with our current local anesthetic to justify its cost.

Objectives:

The primary objective of the study will be to determine the degree of improvement in pain control seen in patients receiving a TQL block in addition to our conventional method of TAP block compared to TAP block alone and intravenous/PO opioids based management. Both groups will have injection of 20 cc 0.25% bupivacaine in the transverse abdominus plane and subcutaneous infiltration of 10 cc around incisions. This is already our standard of care protocol. In addition to this standard care, the study group will receive a TQL block of 20 cc of liposomal bupivacaine mixed with 10 cc of normal saline will be under ultrasound guidance following induction of general anesthesia.

Both groups will have the same bowel preparation, ERAS fluid management, access to antiemetic, opioids, acetaminophen, and NSAIDs on a PRN basis. Assessments of pain scores will utilize the visual analog scale (VAS) evaluated by nursing staff when obtained with the vital signs per PACU and floor nursing protocol. Information regarding use of opioids after discharge will be collected with a pain diary and electronic surveys at least till 90 days. If a patient does not complete their 90 day survey the study team will contact them again to attempt an exit survey.

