Secondary objectives include patient satisfaction scores obtained with a validated satisfaction survey administered to each patient prior to discharge; nausea and vomiting requiring medical intervention; block-related complications noted in the immediate perioperative period or post-operative period; and total opiate requirement during the hospital stay and for 90 days after surgery. We will also monitor the return of bowel function, sexual function and general health using standardized quality of life instruments. Sexual function following kidney donation has not been closely evaluated; yet many patients ask about the potential impact of surgery on this bodily function that is important to a normal quality of life. Each patient will complete the validated survey instruments prior to and after kidney donation. Patients are not required to answer any questions. We will evaluate attitudes toward living kidney donation in relationship to pain control.

Study design/methodology:

This is a randomized, single-blinded controlled trial in patients greater than 18 years of age who have agreed to proceed with laparoscopic donor nephrectomy. Patients meeting these criteria will be offered participation in the study. They will be advised of the risks and potential benefits of the study. They will be advised of the request to answer surveys and have information regarding their care collected for research. They will be advised that participation requires the ability to answer questions using electronic communications. Participation is optional and standard anesthesia and pain control will be provided to all patients. Patients have the option to withdraw

from the study at any time and are not required to answer any of the survey questions. Enrolled patients will not know which treatment is provided.

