The following study variables will be collected postoperatively following arrival in the post-anesthesia care unit: Current and maximum intensity pain scores will be documented by nurses in the electronic medical record (EMR). Total opiate dose consumed every 24 hours will be collected from EMR and electronic survey after discharge. Patient satisfaction will be evaluated using the Revised American Pain Society Patient Outcome Questionnaire (APS-POQ-R) provided on post-operative day 1 by a research assistant or study coordinator. The incidence of nausea or vomiting will be extracted from nursing notes and queried via electronic surveys. Post-discharge, which is typically 1-2 days following surgery, patients will be sent surveys delivered by the UPDW database server 3, 5, 10, 30, and 90 days post-surgery. If patients do not respond 90 days post-surgery study team will contact patients to attempt to have the exit survey completed.

Complications will be documented in the EMR by the anesthesia pain service, urology service, and nurses who will monitor these patients while admitted. Urology and study staff will follow the patients following discharge, including a post-operative office follow-up approximately 1 week post-surgery, as is standard of care

Study Population:

Patients at least 18 years of age undergoing laparoscopic donor nephrectomy. Pregnant patients will be excluded. Patients with local infection at the potential block site or any contraindication to kidney donation, local, or general anesthesia will be excluded.

Study Duration/Study Timeline:

We anticipate a high level of enrollment since most patients have previously consented to having a block placed and pain minimization is generally a high priority. Given the current volume of donor nephrectomies we expect enrollment to be complete within one year. The duration of the study will depend on the timing from consent for surgery until the operation is scheduled. In most cases this occurs within 2-3 months. The study data collections will conclude 90 days after surgery unless the patient was not able to complete the survey. Additional attempt to contact the patient after 90 days post-surgery may be enacted to have the patient(s) complete an exit survey. See the attached study time line in Appendix A.

Statistical Analysis Plan:

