Preliminary power analysis was performed as noted in table 1 below. We believe that utilization of this novel block can produce a pain score reduction of approximately 40% compared to current standard practice. Assuming a study power of 80% and pain score reduction of 40%, we need to enroll approximately 17-20 patients per study arm. However, to demonstrate a clear clinically significant difference we need to enroll over 37 patients per arm. Since some patients may not complete the study, we feel that 50 patients per group will provide sufficient sample size

to determine the benefit versus cost of the study procedure. This is similar to the samples sizes used in the literature.

Pain scores, nausea scores, and total opiate consumption for 24 hours will be analyzed using a T-test of means. Satisfaction will be assessed using a T-test.

Table 1. Power Analysis

Mean 1	Mean 2	Std.	Reduction	Power	n per group
8	4	1	50%	80%	3
7.5	4.5	1	40%	80%	4
7	5	1	29%	80%	6
8	4	2	50%	80%	6
7.5	4.5	2	40%	80%	9
7	5	2	29%	80%	17
8	4	3	50%	80%	10
7.5	4.5	3	40%	80%	17
7	5	3	29%	80%	37

Additional Data Use:

We are interested in using the data collected with this protocol in connection with the CURES Database to analyze the data and investigate whether participants use narcotics prior to donor nephrectomy.

The following will be collected:

1. Historic use of narcotic medication will be collected using the CURES Database (<https://oag.ca.gov/cures>). Patients will be cross-referenced from this study database to the CURES search by name and date of birth. The data points we are searching for are for any narcotic prescription 12 months prior to donor nephrectomy. Also, the date of narcotic prescription closest to date of donor nephrectomy.
2. The milligram morphine equivalent of narcotic medication provided on discharge:
 - a. We will get this information from UCLA CareConnect, and cross-referenced with CURES database.
3. Long-term use of narcotic medication will be collected through the CURES Database. We are collecting to see if they have any narcotic prescriptions in the 0-12 month period after donor nephrectomy excluding discharge prescription. Finally we are finding the furthest narcotic prescription in the 0-12 month period after donor nephrectomy excluding the discharge prescription.

Informed Consent Process:

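### The opioid objective covers the hospital stay and 90 days, but the analysis plan tests consumption only over 24 hours; the 90-day total is the main gap

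*Combined protocol and SAP*

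**What the plan says.** The opioid outcome appears in four parts of the combined protocol and SAP.

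- **Secondary Objectives** gives the aim without a time window: "To determine if narcotic requirements postoperatively are lower in the study group".
- **Objectives** supplies the windows: "total opiate requirement during the hospital stay and for 90 days after surgery".
- **Data collection** matches those windows. Objectives states: "Information regarding use of opioids after discharge will be collected with a pain diary and electronic surveys at least till 90 days". Study design/methodology adds: "Total opiate dose consumed every 24 hours will be collected from EMR and electronic survey after discharge". It places discharge typically 1-2 days after surgery and schedules surveys on days 3, 5, 10, 30 and 90.
- **Statistical Analysis Plan** has two sentences that name tests. One is "Pain scores, nausea scores, and total opiate consumption for 24 hours will be analyzed using a T-test of means". The other assigns a t-test to satisfaction.

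Additional Data Use expresses the discharge prescription in morphine milligram equivalents and lists prescription records for the year after surgery. It names no test, and prescription records do not measure consumption.

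**The concern.** The objective and the analysis use different windows. Followed literally, the analysis would answer the opioid question from 24-hour use, although the objective asks about the whole stay and the following three months.

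The later period matters to the trial's own argument. Background and Significance describes the drug as "designed for prolonged pain relief, up to 72 hours" and sets out to learn whether it gives "opioid-sparing effects, and improved patient satisfaction versus a control group with our current local anesthetic to justify its cost". Twenty-four hours is one third of that 72-hour maximum (24/72).

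The same section reports that six patients given the block with ordinary bupivacaine had good relief for roughly 12-18 hours, "but then had more need for outpatient narcotics after the local anesthetic effect wore off". That observation says nothing about the liposomal drug. It shows only that early and later opioid use can diverge, so a 24-hour result cannot stand in for a 90-day one.

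The windows themselves are already fixed in Objectives. What remains open to choice after the data are seen is how the longer totals are derived and tested.

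**Working it through.** The plan gives no opioid mean, SD or target difference, so there is no opioid figure to reproduce. Its only power figures, in Table 1, concern pain scores. They reproduce: with a two-sided alpha of 0.05 (assumed, since none is stated) and 80% power, a noncentral-t calculation returns all nine group sizes. In the last row the standardised difference is (7 − 5)/3 = 0.667, and the smallest n with at least 80% power is 37 per group. No opioid quantity enters the sample size, so this point leaves it unchanged.

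**Step 1. Compare the objective with the analysis under both readings of the 24-hour phrase.**

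| Quantity | Window named in Objectives | Planned source | If the first 24 hours is meant | If each 24-hour period is meant |
|---|---|---|---|---|
| Hospital-stay total | Yes | EMR | Day 1 tested, remainder not | Daily doses tested, sum not |
| 90-day total | Yes | EMR, then diary and surveys | Nothing after day 1 tested | Daily doses on unspecified days, sum not |
| 24-hour total | No | EMR | Tested | Tested repeatedly |

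**Step 2. Check whether daily tests would amount to a test of the total.** Write D_k for a patient's dose on day k. The difference in mean totals is the sum of the daily mean differences. The variance of the total is Σ Var(D_k) + 2 Σ Cov(D_j, D_k), with the second sum over j < k. Separate daily t-tests do not use the covariances, and the plan gives no rule for combining them. They therefore do not test the cumulative total.

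**Step 3. Size each gap in time covered by 24 hours.**

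- Hospital stay, at the median of 1.4 days given in Background and Significance: 1.4 × 24 = 33.6 hours, and 24/33.6 = 71%.
- Hospital stay, over the typical range of 1-2 days: 24/24 = 100% down to 24/48 = 50%.
- 90 days: 1/90 = 1.1%, leaving 89 days outside the window.

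These are shares of time, not of dose. Use may well be concentrated early, but the documents give no opioid amounts from which to say how much.

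**Step 4. Look for a test elsewhere.** Objectives, Study design/methodology and Additional Data Use describe sources only. None supplies a test for either total.

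**The case against.** **The phrase may mean each 24-hour period**, matching how doses are collected. This is a fair reading. Over a stay of one or two days, one or two tested periods come close to the hospital total. It does not rescue the 90-day total.

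**The objective may describe one running total** from surgery to day 90, not two. The wording allows it. The 90-day quantity would still have no test, so the main gap does not depend on the count.

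**The same t-test is implied for the longer windows.** Perhaps, but the sentence states a different window, and a reader following it would not compute the longer totals.

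**Missing responses are already addressed.** This is partly right. Privacy and confidentiality provides completion monitoring and reminder calls, and Objectives and Study design/methodology provide re-contact of day-90 non-responders. These steps reduce loss. They do not show how many patients end up contributing a complete total.

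**This is one symptom of a short analysis plan.** Quality of life, bowel function and sexual function also have no named test. That is true, but opioid use differs in that the plan states a window and the window conflicts with the objective.

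**Conclusion.** The point holds as a mismatch between a secondary objective and its analysis. The 90-day opioid total has no stated test under either reading. The hospital-stay total has none either, but a 24-hour total covers much of a typical stay, so that gap is small. It should be corrected before the between-arm analysis. It does not threaten the primary pain comparison or the sample size.

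A reader might infer more than the documents support:

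- **That most post-discharge use goes unrecorded because there are only five surveys.** A pain diary is also planned, the recall period of the surveys is not stated, and the questionnaire schedule and Appendix A are not in the text supplied.
- **That the trial is underpowered for opioid use.** With no opioid mean or SD, no such claim can be made in either direction.
- **That the block raises later opioid need.** The preliminary series had six patients, no stated comparison group and a different formulation.

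The conclusion rests on the wording of the sections cited. The only numerical inputs are the stated median stay and the typical discharge time.

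**What to change.** Amend the opioid part of the analysis sentence along these lines:

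> Cumulative opioid consumption, in morphine milligram equivalents, will be compared between arms by t-test of means for the hospital stay and from surgery to day 90. Sources are the EMR until discharge, then the pain diary and electronic surveys. Consumption over 24 hours will also be compared, with the start and end of that period stated.

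The unit is the one Additional Data Use already applies to the discharge prescription. The sentence should also make clear whether the 24-hour limit applies to pain and nausea scores.

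A 90-day total after a one- or two-day stay may be skewed, with many zero days. Add a rank-based or bootstrap comparison as a sensitivity analysis, and report how many patients per arm contribute complete data to each total.

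**Cost.** No extra patients or visits are needed. The change is one of wording, provided the diary and surveys allow a total to be built. Their content is not described in the text supplied and should be checked first. The downside is that post-discharge use is self-reported and some patients will not respond, although reminders and re-contact are already planned.

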Those patients who agree to participate and provide written consent will be enrolled into the study and instructed in the electronic completion of study questionnaires using the Urology Patient Data Waystation (UPDW). Unique, personalized log-in information will be sent to the patient either by email or using the secure MyChart messaging system, based on patient preference, to access UPDW for each time point. Initial questionnaires at enrollment will collect baseline quality of life, bowel and sexual function, and demographic data. When the surgery date has been determined, patients will receive a message to complete a second set of baseline survey questionnaires using the same system if their surgery date is more than 6 months past the date of completion of their initial baseline survey. Those participants who completed their initial baseline within 6 months of their surgery date will only complete one baseline survey.

When surgery is scheduled, each enrolled patient will be randomized (alternating, blocked randomization) to either the study group to receive liposomal bupivacaine TQL block in addition to standard of care post-operative pain management or to the control group to receive our current standard of care. Randomization will maintain equal numbers of participants in each group by sex due to the increased risk of post anesthesia nausea in females.

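### Allocation is balanced by sex, but the planned t-tests leave sex out, so they are slightly conservative wherever sex predicts the outcome

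*Combined protocol and SAP*

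**What the plan says.** Under Study design/methodology, allocation is restricted by sex and the reason is given: "Randomization will maintain equal numbers of participants in each group by sex due to the increased risk of post anesthesia nausea in females". I read this as balance between the arms within each sex.

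The Statistical Analysis Plan names the tests: "Pain scores, nausea scores, and total opiate consumption for 24 hours will be analyzed using a T-test of means". It adds: "Satisfaction will be assessed using a T-test". Neither sentence names a covariate or stratum, and sex enters no analysis anywhere in the document.

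Nausea is a stated target. The Secondary Objectives ask whether "patient-reported nausea and vomiting at post-operative days 1, 3, 5, 10, and 30 is significantly decreased" in the study group. The form of the outcome is less clear. The Statistical Analysis Plan speaks of nausea scores, while Study design/methodology says: "The incidence of nausea or vomiting will be extracted from nursing notes and queried via electronic surveys".

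On size, the Statistical Analysis Plan says "we need to enroll over 37 patients per arm". It then raises this to 50 because of expected losses ("Since some patients may not complete the study"), without giving a dropout rate.

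**The concern.** The design and the analysis do not match. The trial treats sex as prognostic for nausea and spends effort balancing it, and then uses a test that ignores the balance.

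When arms are balanced on a prognostic factor, that factor no longer contributes to chance differences between them. A two-sample t-test still counts the spread between men and women as noise in its standard error. The test therefore rejects less often than its nominal level, and the interval from the same standard error is wider than it needs to be.

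What is at stake is a little precision and power, chiefly for nausea scores. They are the only outcome with both a stated link to sex and a stated t-test.

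**Working it through.** **Inputs from the documents.** 50 per arm, 1:1 (Sample Size). Balance by sex (Study design/methodology). Means 7 and 5, SD 3, 80% power, 37 per group (Table 1, last row). t-tests without covariates (Statistical Analysis Plan).

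**Assumed, because the documents are silent.** Two-sided alpha of 0.05. Equal numbers of men and women. The share of within-arm variance explained by sex, R², set at 0.03, 0.05 and 0.10. With equal numbers of each sex, the sex difference is 2√R² SD, so these are differences of 0.35, 0.45 and 0.63 SD. R² = 0 is equally compatible with the documents. The figure of 45 per arm below illustrates moderate loss.

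**1. The plan's own figure.** The normal approximation gives 2 × (1.960 + 0.842)² × 3² / 2² = 35.3, so 36 per group. The exact t-test calculation gives 37, with power 80.8%. The same method returns the stated n in all nine rows of Table 1. The sample size is sound and is not in question here.

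**2. Variance of the arm difference.** Take the outcome SD as 1 and let n be the number analysed per arm.

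- The t-test's standard error is based on 2/n.
- The true variance is (2/n)(1 − e), with e = R² under exact balance.
- If n of the 50 are kept at random, e = R² × (1 − (50 − n)/49). The multiplier is 1.000 for n = 50, 1 − 5/49 = 0.898 for n = 45, and 1 − 13/49 = 0.735 for n = 37.

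**3. Consequences for the t-test.** Excess interval width is 1/√(1 − e) − 1. Actual type I error is 2 × P(t > t_crit/√(1 − e)) on 2n − 2 degrees of freedom. For n = 50 and R² = 0.05, 1.9845/√0.95 = 2.036, which gives 4.44%. The excess width is 1/√0.95 − 1 = 2.6%.

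| n per arm | R² | Type I error | Interval too wide by |
|---|---|---|---|
| 50 | 0.03 / 0.05 / 0.10 | 4.7 / 4.4 / 3.9% | 1.5 / 2.6 / 5.4% |
| 45 | 0.03 / 0.05 / 0.10 | 4.7 / 4.5 / 4.0% | 1.4 / 2.3 / 4.8% |
| 37 | 0.03 / 0.05 / 0.10 | 4.8 / 4.6 / 4.2% | 1.1 / 1.9 / 3.9% |

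The n = 50 row is the largest departure from nominal; random loss shrinks it. Simulation (400,000 trials per scenario) agrees within about 0.1 percentage points. The model with arm and sex held 4.9% to 5.0% in every scenario. At 50 per arm the average half-width is 0.396 SD for the t-test, against 0.390, 0.386 and 0.376 SD with sex in the model.

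**4. Power, t-test then model with arm and sex** (simulated, 200,000 trials per scenario).

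| Effect | n per arm | R² 0.03 | R² 0.05 | R² 0.10 |
|---|---|---|---|---|
| 0.5 SD (assumed, nausea scores) | 50 | 69.9 to 71.0% | 70.1 to 71.8% | 70.7 to 74.3% |
| 2 points, SD 3 (Table 1, pain) | 50 | 91.3 to 91.8% | 91.5 to 92.2% | 92.0 to 93.5% |
| 2 points, SD 3 (Table 1, pain) | 37 | 81.1 to 81.8% | 81.1 to 82.6% | 81.6 to 84.5% |

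The pain rows apply only if sex predicts pain. At R² = 0, including sex costs 0.2 percentage points of power or less.

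**5. If nausea is yes/no.** With equal numbers of each sex, R² = ((p_F − p_M)²/4) / (p̄(1 − p̄)), where p̄ is the mean of the two incidences. For assumed incidences in women and men:

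- 40% and 30%: R² = 0.0025/0.2275 = 0.011, excess width 0.6%.
- 50% and 30%: R² = 0.0100/0.2400 = 0.042, excess width 2.2%.
- 60% and 30%: R² = 0.0225/0.2475 = 0.091, excess width 4.9%.

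These lie in or below the range used for scores.

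**The case against.** The strongest reply is that nothing here is an error. The t-test is valid and unbiased, and under exact balance the adjusted and unadjusted estimates are identical. The documents do not contradict themselves: one section uses sex to balance, another names a legitimate test. The size depends wholly on an R² that the documents do not supply. Pain is the primary objective, and nothing links it to sex. Power for the smallest Table 1 effect at the largest SD is already about 91% with 50 per arm. The plan promises tests rather than confidence intervals, and the form of the nausea outcome is unsettled. Finally, exact balance and random loss are idealised: no block size, sex mix or dropout rate is given.

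Most of this stands, and it is why the point is optional. The link to sex is documented for nausea only. The figures show a plausible range and do not predict this trial's results. Incomplete blocks or non-random loss would change them.

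Two parts do not carry. First, the absence of a promised interval does not help, because the test and the interval share one standard error, so the mild conservatism is in the plan as written. Second, uncertainty about R² is no reason to leave sex out: the loss if sex is irrelevant is negligible, while the gain if it matters comes almost free.

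**Conclusion.** The concern holds as a minor point of efficiency. Wherever sex predicts the outcome, the planned t-tests are slightly conservative and their intervals slightly too wide. For R² between 0.03 and 0.10, with 50 per arm and exact balance, the interval excess is 1.5% to 5.4%. Power for an assumed 0.5 SD effect on nausea scores would rise by 1.1 to 3.6 percentage points. For the 2-point pain difference the gain is 0.5 to 1.5 points at 50 per arm and 0.7 to 2.9 at 37, and only if sex predicts pain. At R² = 0 all of these effects vanish.

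The direction follows from the algebra and is secure. The size rests on the assumed R², equal numbers of each sex, two-sided alpha of 0.05 and, for the smaller samples, random loss. No conclusion about bias, false positives or sample size follows.

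**What to change.** In the Statistical Analysis Plan, replace the t-tests for pain scores, nausea scores, 24-hour opiate consumption and satisfaction with a linear model of the outcome on arm and sex. Report the adjusted arm difference with its 95% confidence interval. If nausea is analysed as yes/no incidence, for which the plan names no test, use a Mantel-Haenszel risk difference stratified by sex, with its 95% confidence interval. If only one outcome is changed, nausea should be the one.

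The cost is one sentence and one residual degree of freedom: 98 to 97 with 50 per arm, or 72 to 71 with 37. No new data are needed, because allocation already requires the sex of every randomized patient. Writing it down also settles whether sex is adjusted for before results are seen.
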